### Baseline Conditions and Medical History

Information with respect to medical history / baseline conditions will also be collected at Visit 1a (e.g. relevant chronic diseases, current observable conditions and other relevant conditions, based on Investigator judgement, which may not be observable on the day of the examination [e.g. because the patient is receiving concomitant therapy to treat the condition]). This includes any new clinically relevant findings identified during the screening period.

#### **6.2.2 Treatment period(s)**

If a patient is deemed eligible for the trial following Visits 1a, 1b and 1c, the patient will be randomised at Visit 2 (Day 1) by using the IRT system. All Visit 2 assessments (refer to the [Flow Chart](#)) should have been completed prior to administration of the first dose of trial medication; exceptions are the post-dose vital signs and ECGs [REDACTED]  
Each patient can be randomised only once into the trial. The randomised treatment period starts with Visit 2 and ends when a patient reaches the EoT visit (refer to the [Flow Chart](#)). The last dose of BI 685509 will be administered in the evening of the day before the EoT visit and the last dose of empagliflozin in the morning of the day before the EoT visit.

Patients will be assessed regularly at scheduled visits as specified in the [Flow Chart](#). During the dose titration phase of the treatment period (refer to [Section 4.1.4](#)), scheduled visits are more frequent. It is of particular importance that the time window for these visits is adhered to since the patient must have taken the preceding dose of BI 685509 for at least seven consecutive days before any up-titration occurs (refer to Sections [4.1.4](#), [4.1.4.1](#) and [4.1.4.2](#)). Unscheduled visits may also be arranged where necessary; assessments completed during an unscheduled visit will depend on the circumstances under which the visit was planned, and should be based on Investigator judgement.

[REDACTED] Patients should also be reminded to bring [REDACTED] the electronic BP and HR monitoring device with them to each trial visit (refer to [Sections 5.2.2.1](#) and [5.6.1](#)). Refresher training should be provided as required.

At every dispensing visit in the trial (refer to [Flow Chart](#)), an IRT call should be made.

##### **6.2.2.1 End of treatment / Early discontinuation visit**

Patients who successfully complete the entire 8 week treatment period should have the assessments for the EoT visit performed as indicated in the [Flow Chart](#). Such patients should

be registered as completed in the IRT system. End of trial medication must also be recorded on the corresponding eCRF.

For patients who discontinue trial medication prematurely (for whatever reason), an ED visit (refer to the [Flow Chart](#)) should be completed instead of the planned treatment period visit (refer to [Section 3.3.4](#)). Ideally the ED visit should be performed within seven days of discontinuing the trial medication. The assessments performed at the ED visit should be in accordance with the Flow Chart, with the following exceptions:

- HVPG: not required
- [REDACTED]
- biobanking sampling: not required

Patients who discontinue treatment early should be registered as discontinued in the IRT system. End of trial medication must also be recorded on the corresponding eCRF.

At the EoT and / or ED visit, patients should be reminded about restrictions (refer to [Section 4.2.2](#)) that still need to be observed up until the EoS visit (refer to [Section 6.2.3](#)). Home BP and HR monitoring should continue between the EoT / ED visit and the EoS visit.

### **6.2.3 Follow-up period and trial completion**

An EoS visit should be scheduled 4 weeks after an EoT and / or ED visit (refer to the [Flow Chart](#) and [Section 3.3.4](#)); participation in the trial is over once this visit has been completed; completion must be recorded on the corresponding eCRF.

When an EoS visit is performed after an ED visit, the assessments performed at the EoS visit should be in accordance with the Flow Chart, with the following exceptions:

- [REDACTED]

Trial completion is defined as a patient who completes the EoS visit within the specified time window and who has not discontinued trial medication prematurely. Following an EoS visit, the patient will return to standard medical care.

## **7. STATISTICAL METHODS AND DETERMINATION OF SAMPLE SIZE**

In this trial, the primary endpoint is the percentage change in HVPG from baseline (measured in mmHg) after 8 weeks of treatment. The purpose of this trial is to demonstrate the short-time clinical activity of BI 685509 on HBV, HCV and NASH patients.

The effects of BI 685509 will be assessed alone, and in combination with empagliflozin in treatment group 4 (NASH patients with T2DM).

### **7.1 NULL AND ALTERNATIVE HYPOTHESES**

Statistical testing is not planned for this trial. All analyses will be descriptive in nature. The endpoints will be investigated. However, it is not planned to test a statistical hypothesis with regards to these variables in a confirmatory matter. Instead, they will be described and evaluated by descriptive statistical methods.

### **7.2 PLANNED ANALYSES**

#### **7.2.1 General considerations**

[figure not shown]
The analyses will be performed based on the following analysis sets:

- **Enrolled set (ES)** – this analysis set includes all patients having signed informed consent and who were eligible for inclusion into the trial. The ES will be used for analyses of patient disposition
- **Randomised set (RS)** – this analysis set includes all enrolled patients that were entered or randomised to the trial medication. The RS will be used for demographic and baseline disease characteristics presentation
- **Treated set (TS)** – the treated set includes all patients who were enrolled or randomised to the trial medication and were treated with at least one dose. The TS will be used for all safety analyses
- **Full analysis set (FAS)** – this analysis set includes all enrolled or randomised patients who received at least one dose of trial medication and have a baseline measurement for the primary endpoint recorded. The FAS will be used for the efficacy analyses

Further analysis sets will be defined in the TSAP, if needed.

Efficacy analyses will be performed based on the planned treatment (i.e. the treatment assignment at randomisation). Safety analyses will be based on the actual treatment received at the enrolment/randomisation visit.

Unless otherwise stated, baseline is defined as the latest measurement before the first trial medication intake.

## **7.2.2 Handling of intercurrent events**

The expected intercurrent events of interest in this trial are:

- use of the following restricted concomitant therapy:
  - NO-sGC-cGMP pathway activating therapies like NO-donors (e.g. glyceryl trinitrate, isosorbide di- or mono-nitrate, molsidomine), PDE-5-inhibitors (e.g. sildenafil, tadalafil, and vardenafil), non-specific PDE inhibitors such as dipyridamole and theophylline, or sGC-stimulators (e.g. riociguat)
- new onset of / dose change in existing NSBB / carvedilol, pioglitazone, GLP1-agonists and vitamin E concomitant therapy
- occurrence of a decompensation event
- Premature discontinuation of assigned trial medication

The strategies for handling intercurrent events in this trial are as follows:

Treatment Policy: This is the effect of randomizing patients to a treatment arm regardless of treatment actually being taken. All intercurrent events will be handled according to the treatment policy approach as defined in ICH E9(R1).

Each analysis will reference the strategy for handling intercurrent events that it will be estimating. The estimand for each main analysis in this protocol is the combination of the relevant detailed clinical objective from [Section 2.1](#) and this strategy.

Handling of the intercurrent events that are not listed above will be decided by the review and will be documented in the TSAP.

### 7.2.3 Primary objective analyses

The primary endpoint (refer to [Section 2.1.2](#)) will be analyzed using an ANCOVA model in the FAS without imputing the missing data.

The model is as follows:

Percentage of HVPG change from baseline at Week 8 = overall mean  
+ HVPG baseline  
+ treatment  
+ random error

This model includes effects accounting for the following sources of variation: ‘treatment’ is a fixed classification effect, and ‘HVPG at baseline’ is a linear covariate. The random error is assumed to be normally distributed with mean 0 and unknown variance  $\sigma^2$ .

The analysis will only be used for estimation of treatment effects without performing statistical tests. Patients will be analysed according to the stratum to which they belong (regardless of any mis-assignment to treatment based on identification of the wrong stratum), as such an error occurs before randomisation and is therefore consistent with regulatory guidance. Procedures to follow if the analysis fails to converge will be described in the TSAP.

#### 7.2.3.1 Sensitivity analyses

Sensitivity analyses may be performed and will be described in more detail in the TSAP, if applicable.

#### 7.2.3.2 Subgroup analyses

Any subgroup analyses planned for this trial will be described in the TSAP, if applicable.

### 7.2.4 Secondary objective analyses

Unless otherwise stated, only descriptive statistics will be presented for the secondary endpoints defined in [Section 2.1.3](#). The percentage of patients who have experienced the events of interest for secondary endpoints will be presented.

### **7.2.5      Further objective analyses**

Only descriptive statistics will be presented for further endpoints (defined in [Section 2.2.2](#)).

### **7.2.6      Safety analyses**

Adverse events will be coded using the Medical Dictionary for Drug Regulatory Activities (MedDRA). Standard BI summary tables and listings will be produced. All adverse events with an onset between start of treatment and end of the REP, a period of 7 days after the last dose of trial medication, will be assigned to the on-treatment period for evaluation.

[figure not shown]
Safety analyses will be done by “treatment at onset” principle. All treated patients will be included in the safety analysis. In general, safety analyses will be descriptive in nature and will be based on BI standards. No hypothesis testing is planned.

Statistical analysis and reporting of adverse events will concentrate on treatment-emergent adverse events, i.e. all adverse events occurring between start of treatment and end of the REP. Adverse events that start before first drug intake and deteriorate under treatment will also be considered as ‘treatment-emergent’.

Frequency, severity, and causal relationship of adverse events will be tabulated by system organ class and preferred term after coding according to the current version of the Medical Dictionary for Drug Regulatory Activities (MedDRA) at database lock.

Laboratory data will be analysed both quantitatively as well as qualitatively. The latter will be done via comparison of laboratory data to their reference ranges. Values outside the reference range as well as values defined as clinically relevant will be summarised. Treatment groups will be compared descriptively with regard to distribution parameters as well as with regard to frequency and percentage of patients with abnormal values or clinically relevant abnormal values.

Vital signs, physical examinations, or other safety-relevant data observed at screening, baseline, during the course of the trial and at the end-of-trial evaluation will be assessed with regard to possible changes compared to findings before start of treatment.

### **7.2.8      Interim analyses**

No interim analysis is planned but a Data Monitoring Committee (DMC) will be in place with tasks as described in [section 8.7](#). Full details will be specified in the DMC charter. The primary role of the DMC is the ongoing evaluation of safety.

### **7.3            HANDLING OF MISSING DATA**

No imputation of missing data is planned for the remaining endpoints. If a patient misses a visit, the missing data will not be imputed.

### **7.4            RANDOMISATION**

BI will arrange for the randomisation and the packaging and labelling of trial medication. A minimum of 40 NASH patients (either with or without a diagnosis of T2DM) will enter treatment group 3 or 4. NASH patients without diagnosis of T2DM can only enter treatment group 3, while NASH patients with diagnosis of T2DM will be randomized in blocks to one of the two treatment groups (treatment group 3 or treatment group 4) in a 1:1 ratio.

The randomisation list will be generated using a validated system, which involves a pseudo-random number generator so that the resulting treatment will be both reproducible and non-predictable. The block size will be documented in the Clinical Trial Report. Access to the codes will be controlled and documented.

### **7.5            DETERMINATION OF SAMPLE SIZE**

It is planned to enroll 80 patients with HBV, HCV and NASH in total in this trial with a minimum of 20 NASH patients in treatment group 3 (with or without T2DM receiving [REDACTED] BI 685509) and a minimum of 20 NASH patients in treatment group 4 (with T2DM receiving [REDACTED] BI 685509 on top of 10mg empagliflozin).

It will be considered as a positive signal if a mean reduction of HVPG after 8 weeks of treatment compared to baseline of at least 15% is observed. A true treatment effect of 20% reduction for each treatment group and a standard deviation of 25% are assumed based on previous studies [[R21-1984](#), [R21-1945](#)]. With the minimum sample size of 20 per arm in treatment group 3 and 4, the probability to observe a mean reduction of HVPG  $\geq 10\%$  in each of the treatment groups 3 and 4 is at least 96.3%. This probability would be at most 18.8% in case that the mean reduction of HVPG from baseline is 5%. Probabilities of achieving an assumed treatment effect within different scenarios are presented in Table [7.5: 1](#).

Table 7.5: 1

Scenarios of probabilities of achieving the assumed treatment effect

Scenarios	Assumption of mean reduction in HVPG from baseline to week 8	Probability that the treatment effect is <math>\geq 10\%</math> per arm in treatment group 3 and 4
Positive	20%	at least 96.3%
	15%	at least 82%
Negative	5%	at most 18.8%
	0%	at most 3.8%

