#### **2.1.3 Secondary endpoint(s)**

Secondary endpoints include:

- occurrence of a response, which is defined as > 10% reduction from baseline HVPG (measured in mmHg) after 8 weeks of treatment
- occurrence of one or more decompensation events (i.e. ascites, VH, and / or overt HE) during the 8-week treatment period
- occurrence of CTCAE grade 3 (or higher) hypotension or syncope based on Investigator judgement, during the 8-week treatment period
- occurrence of discontinuation due to hypotension or syncope during the 8-week treatment period

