1 SD = 25%

2 N  $\geq 20$  per arm in treatment group 3 and 4

The calculations were performed using R 4.0.2.

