**4. CHANGES IN THE PLANNED ANALYSIS OF THE STUDY**

There are no changes in this TSAP compared to the statistical methods described in the CTP.

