#### **7.4.1 Main analysis**

For the primary endpoint, the analysis of covariance (ANCOVA) will be used. The analysis will be performed on the FAS and include on-treatment HVPG only. If a patient misses the Week 8 visit, the missing data will not be imputed.

[figure not shown]
The statistical model will be:

Percentage HVPG change from baseline at Week 8 = overall mean + HVPG baseline + treatment + random error

This model includes treatment as fixed classification effects and baseline HVPG as a linear covariate. The random error is assumed to be normally distributed with mean 0 and variance  $\sigma^2$ . The analysis will only be used for estimation of treatment effects without performing statistical tests.

The main analysis will implement the primary estimand defined in [Section 6.3](#) and be performed on FAS. All data collected after the intercurrent events will be used for the analysis. The number of patients reporting each type of intercurrent event will be summarized for overall and each treatment group.

If after all the steps above have been investigated without successful model convergence, then an ANCOVA (Analysis of Covariance) model at Week 8 only, will be performed. If the above sequence of methods does not lead to convergence for a particular subgroup, then that analysis will not be performed or reported.

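### Protocol Section 7.5 sets the positive signal at an observed mean HVPG reduction of at least 15%, but every probability it gives is for at least 10%

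*Protocol*

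**What the plan says.** Protocol Section 7.5 plans 80 patients, with at least 20 in each of treatment groups 3 and 4. It assumes a true 20% reduction and an SD of 25%. It then counts the outcome as a "positive signal if a mean reduction of HVPG after 8 weeks of treatment compared to baseline of at least 15% is observed".

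The next sentences use a different threshold. For an observed mean reduction of 10% or more, the probability "in each of the treatment groups 3 and 4 is at least 96.3"%, falling to at most 18.8% if the true reduction is 5%. Table 7.5:1 does the same. Its result column, headed "Probability that the treatment effect is" 10% or more, gives at least 96.3%, at least 82%, at most 18.8% and at most 3.8% for true reductions of 20, 15, 5 and 0%. The footnotes give the SD of 25% and a sample size of 20 or more "per arm in treatment group 3 and 4".

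The SAP sets no threshold for a mean reduction and says: "There are no changes in this TSAP compared to the statistical methods described in the CTP". The only other 10% in this context is the secondary endpoint in Protocol Section 2.1.3, "occurrence of a response, which is defined as > 10% reduction from baseline HVPG (measured in mmHg) after 8 weeks of treatment".

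**The concern.** A reader takes Table 7.5:1 as the operating characteristics of the signal rule stated just above it, but the two use different cut-offs. In the table, 15% appears only as an assumed true mean, never as the observed cut.

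This matters because the trial has no placebo arm and no hypothesis test. The 15% sentence is the only numerical criterion for reading the primary result, and the table is the only numerical support for the sample size. An arm with an observed mean reduction between 10% and 15% is a signal under one threshold and not under the other. If that is left open, the choice could be made after open-label data have been seen.

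**Working it through.** **Inputs.** All come from Protocol Section 7.5 and the footnotes to Table 7.5:1: SD 25%, n = 20 per arm, true reductions μ of 20, 15, 5 and 0%, and observed cuts c of 10% (text and table) and 15% (signal sentence).

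**Formula.** For a single-arm mean under a normal model, P(observed mean ≥ c) = Φ((μ − c)/SE), with SE = 25/√20 = 5.590.

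**Step 1: reproduce the plan's figures (c = 10).**
- μ = 20: Φ(10/5.590) = Φ(1.789) = 96.3%
- μ = 15: Φ(5/5.590) = Φ(0.894) = 81.4%
- μ = 5: Φ(−0.894) = 18.6%
- μ = 0: Φ(−1.789) = 3.7%

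The plan states 96.3, 82, 18.8 and 3.8%. The table was therefore calculated for the 10% cut, one arm at a time. If both arms had to reach 10% and were independent, the first figure would be 0.9632² = 92.8%. As bounds, 'at most' 18.8% and 3.8% hold. 'At least' 82% does not quite hold at n = 20, where the value is 81.4%.

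**Step 2: apply the stated rule (c = 15).**
- μ = 20: Φ(0.894) = 81.4%
- μ = 15: Φ(0) = 50.0%
- μ = 5: Φ(−1.789) = 3.7%
- μ = 0: Φ(−15/5.590) = Φ(−2.683) = 0.4%

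No row matches the table. The second row settles the matter without reference to n or SD: when the true mean equals the cut, the probability is 50% at any sample size. A table showing 82% there cannot describe a 15% cut.

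**Step 3: how often the two thresholds disagree.** P(10 ≤ observed mean < 15) is the difference between the two results, shown in the last column (from unrounded values).

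| True reduction | Stated in table | Cut 10% | Cut 15% | Mean between 10% and 15% |
|---|---|---|---|---|
| 20% | at least 96.3% | 96.3% | 81.4% | 14.9% |
| 15% | at least 82% | 81.4% | 50.0% | 31.4% |
| 5% | at most 18.8% | 18.6% | 3.7% | 14.9% |
| 0% | at most 3.8% | 3.7% | 0.4% | 3.3% |

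**Step 4: fewer evaluable patients.** Protocol Section 6.2.2.1 lists, for the early discontinuation visit, "HVPG: not required". SAP Section 7.4.1 adds: "If a patient misses the Week 8 visit, the missing data will not be imputed". The 20 per arm are therefore not necessarily 20 with a Week 8 value. Section 7.5 states no dropout rate, so 18 and 16 are assumptions chosen to show a range.

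| Evaluable n | SE | Cut 10%, μ = 20 / 15 / 5 / 0 | Cut 15%, μ = 20 / 15 / 5 / 0 |
|---|---|---|---|
| 18 | 5.893 | 95.5 / 80.2 / 19.8 / 4.5% | 80.2 / 50.0 / 4.5 / 0.5% |
| 16 | 6.250 | 94.5 / 78.8 / 21.2 / 5.5% | 78.8 / 50.0 / 5.5 / 0.8% |

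This effect is small beside the effect of the threshold.

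**The case against.** The strongest reply is that little depends on the sentence. Protocol Section 7.1 rules out statistical testing, no interim analysis is planned, and the SAP contains no signal threshold, so no programmed output would change. The table is correctly calculated for its own labelled cut. The sample size is also defensible under either reading: at the assumed 20% effect the 15% rule still gives 81.4% per arm, and its false-signal chance at a true 5% is about one fifth of that under the 10% rule. Finally, Protocol Section 3.2 gives another basis for interpretation, an indirect comparison with the Week 8 results of trial 1366-0021.

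All of that is true, and it limits the consequence to planning and interpretation. It does not remove the contradiction. The comparison in Section 3.2 carries no numerical criterion. The 10% in Section 2.1.3 defines response in one patient, not a group mean. A two-tier reading, with 15% as the signal and 10% as a minimum, is not written anywhere and would still leave the named criterion without a probability.

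The amendment history shows that Amendment 1 corrected 96.4% to 96.3% in this section to agree with the table and kept the 10% threshold. That is weak evidence that 10% was the working cut for the calculation. It does not show that the 15% sentence is the mistake.

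**Conclusion.** The concern holds. The stated rule and the supporting figures use different thresholds, and nothing in the protocol or SAP reconciles them. If 15% is the rule, the chance of a signal at the assumed 20% effect is 81.4% per arm, not 96.3%. At a true 15%, which the table lists as a positive scenario, it is 50.0%. The false-signal chance at a true 5% is 3.7%, against 18.6% for the 10% cut (stated as at most 18.8%). If 10% was meant, the text as written would deny a signal to an arm with a mean between 10% and 15%, which happens with probability 14.9% at a true 20% and 31.4% at a true 15%.

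These figures rest on the protocol's SD of 25%, normality of the arm mean and 20 evaluable patients per arm. The documents do not show which threshold was intended. The primary estimate and its ANCOVA are unaffected.

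**What to change.** Use one threshold throughout Section 7.5.

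- **If 15% stands:** change the cut in the text and in the Table 7.5:1 header to 15%, and replace the figures with at least 81.4%, 50.0%, at most 3.7% and at most 0.4% for true reductions of 20, 15, 5 and 0%. The 50.0% holds at any n, so reconsider the 'Positive' label on that row.
- **If 10% was intended:** change 15% to 10% in the signal sentence, and 82% to 81.4% in the table.

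In both cases state that the figures are per arm and assume 20 patients with an evaluable Week 8 HVPG.

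The cost is protocol wording only, with no extra patients. Keeping 15% means restating four figures and accepting a lower chance of a signal (96.3% to 81.4% at a true 20%) in return for a lower chance of a false one (18.6% to 3.7% at a true 5%). Keeping 10% changes one threshold and one figure.

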### **3.3.4 Discontinuation of patients from trial medication and assessments**

Patients may discontinue trial treatment after enrolment or withdraw consent to trial participation as a whole (“withdrawal of consent”) with very different implications; please see sections [3.3.4.1](#) and [3.3.4.2](#) below.

However, if the patients agree, they should stay in the trial. Even if continued trial treatment is not possible, they should attend further trial visits to ensure their safety and to collect important trial data.

Measures to control the withdrawal rate include careful patient selection, appropriate explanation of the trial requirements and procedures prior to trial enrolment, as well as the explanation of the consequences of withdrawal.

The decision to discontinue trial treatment or withdraw consent to trial participation and the reason must be documented in the patient files and CRF. If applicable, consider the requirements for Adverse Event collection reporting (please see [section 5.2.6.2](#)).

Patients who discontinue after randomisation will not be replaced and may not be re-enrolled later. However, the Sponsor may decide to randomise more patients than originally planned, to account for a reduced sample size, if patients terminate early due to e.g. trial disruption (such as measures to control a global pandemic).

---

 Examples of medical conditions may include, but are not limited to: symptomatic heart failure (New York Heart Association [NYHA] III/IV), known history of tachycardia, clinically relevant arrhythmias, coronary heart disease not compensated by medical treatment (existing unstable angina pectoris)

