## **5. ENDPOINTS(S)**

### **5.1 PRIMARY ENDPOINT(S)**

The primary endpoint is the percentage change in HVPG from baseline (measured in mmHg) after 8 weeks of treatment.

The calculation of HVPG will be based on the measurements of wedged hepatic venous pressure (WHVP) and free hepatic venous pressure (FHVP).

The average WHVP and the average FHVP will be calculated from the triplicate measurements. Either the average FHVP or the measurement proximal free hepatic venous pressure (PFHVP) will be used as the subtrahend for the calculation of HVPG, which will be rounded to one decimal place.

Based on the judgement of the central reader, if the recorded PFHVP is considered to be more reliable than the average of the recorded triplicate FHVPs, then:

$$\text{HVPG (mmHg)} = \text{average WHVP (mmHg)} - \text{PFHVP (mmHg)};$$

if the average of the recorded triplicate FHVPs is considered to be more reliable than the recorded PFHVP, then

$$\text{HVPG (mmHg)} = \text{average WHVP (mmHg)} - \text{average FHVP (mmHg)}.$$

The quality of the HVPG will be categorized into optimal, sub-optimal and not evaluable based on the judgement of the central reader. A frequency table will be provided to summarize the quality of HVPG tracings measured at baseline and week 8.

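### Table 7.5:1 ties its probability bounds to 20 patients entered per arm, not 20 with evaluable HVPG, and its 15% row is slightly wrong even with no loss

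*Protocol*

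**What the plan says.** Protocol Section 7.5 plans for 80 patients, with at least 20 NASH patients in each of groups 3 and 4. Its planning inputs are "A true treatment effect of 20% reduction for each treatment group" and "a standard deviation of 25% are assumed based on previous studies". The key sentence begins "With the minimum sample size of 20 per arm in treatment group 3 and 4, the probability to observe a mean reduction of HVPG" and gives at least 96.3% for an observed mean reduction of 10% or more. Table 7.5:1 gives, per arm, at least 96.3%, at least 82%, at most 18.8% and at most 3.8% for true reductions of 20%, 15%, 5% and 0%. The same section calls an observed mean reduction of at least 15% a positive signal.

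Other sections determine how many of those 20 reach the primary analysis:

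- Protocol 6.2.2.1, early discontinuation visit: "HVPG: not required".
- Protocol 3.3.4: "Patients who discontinue after randomisation will not be replaced and may not be re-enrolled later". The next sentence lets the sponsor randomise more patients if some terminate early, at its discretion and with no number given.
- Protocol 7.2.3: the primary endpoint "will be analyzed using an ANCOVA model in the FAS without imputing the missing data". SAP 7.4.1 repeats that a missed Week 8 value is not imputed and restricts the analysis to on-treatment HVPG.
- SAP 5.1: "The quality of the HVPG will be categorized into optimal, sub-optimal and not evaluable", on the central reader's judgement.

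**The concern.** The table's *at least* and *at most* are guarantees that depend on N. The N used counts patients entered; the mean that will be reported is taken over patients with two usable HVPG values. Nothing in Section 7.5 links the two: it gives no dropout rate, no rate of unreadable tracings and no evaluable target.

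Some loss is foreseeable. The measurement is invasive and done twice. Protocol 3.3.4.1 lists several mandatory reasons to stop treatment. Eligibility rests on the local reading of the baseline tracing while the central reading is the official one (Protocol 5.1.1), so a baseline value could also be lost.

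Because "Statistical testing is not planned for this trial", Section 7.5 is the plan's only numerical statement of how well the trial separates an active from an inactive treatment. Its figures should describe the number of patients actually averaged.

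**Working it through.** **Inputs.** SD 25%; true reductions 20, 15, 5 and 0%; threshold 10%; N = 20 per arm (all Protocol 7.5 and Table 7.5:1 with its footnotes). The loss rate is not in the documents; the values below 20 are assumptions.

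**Formula.** For one arm, P(observed mean reduction ≥ c) = Φ((μ − c) / (25/√N)).

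**Reproducing the plan's figures.** At N = 20 the standard error is 25/√20 = 5.59.

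- μ = 20: Φ(10/5.59) = Φ(1.789) = 96.3%
- μ = 15: Φ(5/5.59) = Φ(0.894) = 81.4%
- μ = 5: Φ(−0.894) = 18.6%
- μ = 0: Φ(−1.789) = 3.7%

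This is evidently the calculation behind the table. Three of the four bounds hold. *At least 82%* does not: at N = 21, Φ(5/5.455) = 82.0%, so it needs 21 patients. The table also fails an internal check. The 15% and 5% rows lie symmetrically about the 10% threshold, so with equal N they must add to 100%; they add to 82 + 18.8 = 100.8%.

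**Effect of loss, threshold 10%, per arm.**

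| Evaluable N | True 20% | True 15% | True 5% | True 0% |
|---|---|---|---|---|
| Stated | ≥ 96.3 | ≥ 82 | ≤ 18.8 | ≤ 3.8 |
| 20 | 96.3 | 81.4 | 18.6 | 3.7 |
| 19 | 95.9 | 80.8 | 19.2 | 4.1 |
| 18 | 95.5 | 80.2 | 19.8 | 4.5 |
| 17 | 95.1 | 79.5 | 20.5 | 5.0 |
| 16 (20% loss) | 94.5 | 78.8 | 21.2 | 5.5 |
| 15 (25% loss) | 93.9 | 78.1 | 21.9 | 6.1 |

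At 19, the three bounds that held at 20 are missed by 96.3 − 95.9 = 0.4, 19.2 − 18.8 = 0.4 and 4.1 − 3.8 = 0.3 points. The 15% row, already short by 82 − 81.4 = 0.6, is now short by 1.2. A row is first more than 2 points from its stated value at 17 evaluable (82 − 79.5 = 2.5); all four are at 15.

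**Same formula at the declared 15% signal threshold.**

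| Evaluable N | True 20% | True 15% | True 5% | True 0% |
|---|---|---|---|---|
| 20 | 81.4 | 50.0 | 3.7 | 0.4 |
| 18 | 80.2 | 50.0 | 4.5 | 0.5 |
| 16 | 78.8 | 50.0 | 5.5 | 0.8 |

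At the planning effect of 20%, the change of threshold (96.3% to 81.4% at N = 20) matters far more than the loss of a few patients.

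**The case against.** The best defence is that 20 is a floor. The table's footnote says N ≥ 20, and the amendment rationale allows groups 3 and 4 to exceed it. Group 3 probably will: NASH patients with T2DM are split 1:1 between groups 3 and 4, and every NASH patient without T2DM also goes to group 3. An arm that enters 21 and loses one has exactly the 20-patient figures, and the sponsor may randomise more. This stands as a limit on the point. It does not remove it, because the floor is still a floor on patients entered, and the option to add patients is neither required nor quantified.

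Four stronger readings are tempting, and the documents do not support them.

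- *One missing value breaks every bound.* The 15% row already fails at 20, so the loss breaks only the other three. The move from 20 to 19 shifts each figure by only 0.4 to 0.6 points.
- *The 96.3% should be 92.8%, the chance that both arms pass (0.963² with independent arms).* The text's wording is loose, but the table header says per arm, and no rule requires both arms to succeed.
- *The risk of a false signal exceeds what is stated.* That is true only at the table's 10% threshold. At the protocol's own 15% criterion, the probabilities under a true 5% or 0% reduction are 3.7% and 0.4% at N = 20, and 5.5% and 0.8% at N = 16. All are below the tabulated 18.8% and 3.8% for the same scenarios.
- *The trial is too small.* There is no test and no power target, so nothing here calls for more patients.

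**Conclusion.** The point holds as a correction to Section 7.5. Two things are established. First, *at least 82%* is wrong at the stated minimum: the value is 81.4%, whatever is assumed about loss. Second, the bounds apply to 20 evaluable patients per arm, and the plan neither secures nor estimates that number. If an arm ends with 19, none of the four statements is true as written, although the shortfall is small: 0.3 to 0.4 points on three rows and 1.2 on the fourth. At an assumed 20% loss from 20 entered, the figures are 94.5 / 78.8 / 21.2 / 5.5%.

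These results rest on the protocol's SD of 25%, a normal mean within one arm without covariate adjustment, and an assumed loss. They also assume that a tracing graded not evaluable yields no HVPG value, which SAP 5.1 implies but does not spell out. No error rate, estimate or recruitment target changes.

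**What to change.** In Protocol Section 7.5 and Table 7.5:1:

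1. Give the probabilities by number of patients per arm with evaluable baseline and on-treatment Week 8 HVPG, for example 20, 18 and 16.
2. Correct the 15% row at N = 20 to 81.4%. The 5% and 0% rows can then be shown as 18.6% and 3.7%.
3. Tie *at least* and *at most* explicitly to the evaluable number.
4. Say per arm in the text, as the table header does.
5. Show the probabilities at the declared 15% signal threshold beside those at 10%.

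The cost is a text and table edit. No extra patients are needed; the only downside is that the figures look slightly less favourable.
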